#### **11.1.1.4 Overdose**

A drug overdose is defined as the accidental or intentional use of a drug or medicine or an administration error in an amount that is higher than is normally used. Every overdose must be reported to the designated pharmacovigilance/safety services within 24 hours of awareness, irrespective of whether the overdose was associated with an AE/SAE.

Overdose in this study is specifically defined as any dose greater than the intended protocol dose ([Section 10.1.1](#)). In case of overdose, it is recommended that the subject be monitored for any signs or symptoms of adverse reactions or effects and appropriate symptomatic treatment be instituted immediately.

#### **11.1.1.5 Product Quality Complaint**

A product quality complaint (PQC) is related to a potential quality issue during manufacturing, release testing, stability monitoring, dose preparation, storage, or distribution of the product or delivery system. In addition, it includes any reports in which a suspicion of counterfeit/tampering exists. It is important to note that not all PQCs involve a subject. A PQC should be reported within 24 hours, using the details provided in [Section 11.1.2](#).

#### **11.1.1.6 Planned Hospitalization**

A hospitalization planned by the subject prior to signing the ICF is considered a therapeutic intervention and not the result of a new SAE and should be recorded as medical history. If the planned hospitalization or procedure is executed as planned, the record in the subject's medical history is considered complete. However, if the event/condition worsens during the study, it must be reported as an AE.

#### **11.1.1.7 Incident**

A device-related incident is any product complaint that led to or might have led to death or serious deterioration of health/serious injury/serious illness for the user of the product or any other person. Note that "device" refers to the [REDACTED] for this study. The incident should be reported within 24 hours, using the details provided in [Section 11.1.2](#).

#### **11.1.1.8 Recording of Adverse Events**

Any relevant observations made before the end of the Baseline visit (prior to signing the ICF for this long-term extension study) are to be recorded on the AE eCRF, but will not be considered TEAEs and will be reported separately from TEAEs. Any relevant observations

made after signing the ICF will be recorded as an AE in the subject's AE eCRF (see [Section 11.1.1.1](#)).

For the purposes of this study, any detrimental change in the subject's condition, after the first dose of IMP for the long-term extension study and up to completion of the EoT/Follow-up visit, should be considered an AE.

The following variables will be recorded for each AE: verbatim/AE description and date for AE start and stop, intensity, seriousness, causality rating, whether or not the AE caused the subject to discontinue, and the outcome. A new AE must be recorded if the intensity of the AE changes.

All AEs/SAEs have to be reported to the Sponsor, whether or not considered causally related to the IMP or to the study procedure(s).

All ongoing AEs/SAEs should be followed up until resolution or stabilization or the last visit if in the Investigator's opinion, the AE is unlikely to resolve due to the subject's underlying disease.

At any time after the subject has taken the first dose of IMP, if an Investigator learns of an SAE that can be reasonably related to IMP, he/she should promptly notify the Sponsor.

The Investigator will assess the intensity of AEs based on the following definitions:

- Mild (awareness of sign or symptom, but easily tolerated),
- Moderate (discomfort sufficient to cause interference with normal activities),
- Severe (incapacitating, with inability to perform normal activities).

It is important to distinguish between serious and severe AEs. Severity is a measure of intensity whereas seriousness is defined by the criteria in [Section 11.1.1.2](#).

An AE of severe intensity need not necessarily be considered serious. For example, nausea that persists for several hours may be considered severe nausea, but not an SAE. On the other hand, a stroke that results in only a limited degree of disability may be considered a mild stroke but would be an SAE.

For an AE to be a suspected drug-related event, there should be at least a reasonable possibility of a causal relationship between the IMP and the AE.

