In PsA Phase 2 study [CLR\_16\_23 PsA study], both tildrakizumab, 200 mg q12 weeks and tildrakizumab 100 mg, q12 weeks provided similar efficacies in the ACR20, ACR50, and ACR70 at Week 24. The lowest dose of 20 mg q12 weeks, did not demonstrate superiority over placebo in ACR70 and had numerically lowest ACR 50 response among the active doses tested. The highest dose of tildrakizumab 200 mg q4 weeks, did not provide significant benefit over tildrakizumab 200 mg, q12 weeks. Therefore, the dose regimen of tildrakizumab 100 mg, q12 weeks is chosen for the long-term extension study going forward.

Subjects not deriving sufficient clinical benefit in the opinion of the Investigator at any time after the initiation of this long-term extension study should be discontinued from IMP as described in [Section 9.3.5](#), and receive clinical care as determined by the Investigator.

With the exception of those who withdraw informed consent, subjects who withdraw from IMP during the long-term extension study, will undergo the EoT assessments approximately

4 weeks after their last administration of IMP. Subjects who complete treatment to Week 200 will return for a Follow-up assessment at Week 208 (4 years).

The primary safety objectives of this study include assessment of the long-term safety of tildrakizumab by evaluation of incidence and intensity of AEs, and changes in vital signs, laboratory assessments, ECGs, C-SSRS, and immunogenicity data.

No independent assessor is needed to assess efficacy measurements. There will be no efficacy assessments during the LTE study. The Principal Investigator (PI)/designee will be responsible for performing safety evaluations.

Clinical Adjudication Committee (CAC) will be established to evaluate cardiovascular events ([Section 13.3.6](#)).

End of study is defined as the last visit of the 4-year treatment period (Week 208, EoT/Follow-up) for the last global subject.

This study will be conducted in compliance with the protocol and with the International Council for Harmonisation (ICH) of Technical Requirements for Pharmaceuticals for Human Use guidelines on Good Clinical Practice (GCP).

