- d To include body weight and height only. Other demographic data including date of birth, sex, and ethnicity will be obtained from the parent study.
- e Report all AEs, SAEs, and concomitant medications that occur after signing of the Informed Consent Form for the long-term study. Any occurring prior to signing the Informed Consent Form for the long-term study should be recorded under Medical/Medication history.
- f IMP administration will occur on Day 1 of Week 0; followed by subsequent dosing Q12 weeks.
- g Blood samples are to be collected (pre-dose where applicable), after ECG and vital sign measurements.
- h At visits where lipids are assessed, the blood samples are to be collected (pre-dose where applicable) after 12 hours fasting, following ECG and vital sign measurements.
- i Urine pregnancy tests will be performed by using a urine dip stick. ESR will be performed at the site using materials supplied by the central laboratory. hsCRP samples will be sent to the central lab and analyzed by central lab.
- j A final anti-drug antibodies sample needs to be collected after 20 weeks from last dose.
- k Evaluations will continue from the parent study using the version with questions referring to 'since the last visit'. No lifetime version will be repeated at BL.

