#### **9.1.3.1.3 End of Treatment/Follow-Up (Week 208 or Approximately 4 Weeks after Last Investigational Medicinal Product Administration)**

Subjects who complete the study and receive the last scheduled IMP administration at Week 200 will return for a final Follow-up assessment at Week 208 (4 years). In addition,

subjects who withdraw from IMP at any time during this long-term extension study will return for the EoT/Follow-up assessment approximately 4 weeks after administration of their last dose of IMP.

The assessments and procedures listed in [Table 9-1](#) will be performed and include:

- Record physical examination findings.
- Perform a urine pregnancy test by urine dip stick (at the site using materials supplied by the central laboratory).
- Perform safety assessments including:
  - 12-lead ECG,
  - vital signs,
  - C-SSRS,
  - routine safety laboratory assessments (hematology, chemistry, and urinalysis),
  - lipids,
- hsCRP and ESR measures, to be used for determination of potential AEs should they rise unexpectedly (ESR will be performed at the site using materials supplied by the central laboratory. CRP samples will be sent to the central lab and analyzed by central lab),
  - AEs,
  - record concomitant medications.
- Obtain a PK sample.
- Obtain a blood sample for ADA assessments. A final ADA sample needs to be collected after 20 weeks from last dose.

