#### **9.3.2 Exclusion Criteria**

Subjects should be excluded from the study if they meet any of the following criteria:

1. New onset during the parent study of arthritic conditions other than the subject's original condition.
2. Female subjects of childbearing potential who do not agree to abstain from heterosexual activity or practice a dual method of contraception, for example, a combination of the following: (1) oral contraceptive, depo-progesterone, or intrauterine device; and (2) a barrier method (condom or diaphragm). Male subjects with female partners of childbearing potential who are not using birth control as described above must use a barrier method of contraception (e.g., condom) if not surgically sterile (i.e., vasectomy). Contraceptive methods must be practiced upon entering the study and through 16 weeks after the last dose

of IMP. If a subject discontinues prematurely, the contraceptive method must be practiced for 16 weeks following final administration of IMP.

3. Female is pregnant or breastfeeding, or planning to become pregnant or initiate breastfeeding while enrolled in the study or up to 16 weeks after the last dose of IMP.
4. Subject has previously been enrolled in this long-term extension study.
5. Any condition that in the opinion of the Investigator represents an obstacle for study conduct and/or represents a potential unacceptable risk for the subject.
6. Subject has an active infection or history of infections as follows:
  - a serious infection, defined as requiring hospitalization or intravenous anti-infectives within 8 weeks prior to the first IMP dose of the extension study, with the last dose having been received within 7 days of start of the extension study,
  - recurrent or chronic infections, e.g., chronic pyelonephritis, chronic osteomyelitis, bronchiectasis, or other active infection that, in the opinion of the Investigator, might cause this extension study to be detrimental to the subject.
7. Major chronic inflammatory or connective tissue disease other than PsA (e.g., rheumatoid arthritis, systemic lupus erythematosus, Lyme disease, or gout, Crohn's disease, etc).
8. Known diagnosis of fibromyalgia, regional pain syndromes or active uveitis/symptomatic inflammatory bowel disease requiring therapy.

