### **9.3.5      Investigational Medicinal Product Discontinuation**

Subjects may voluntarily discontinue IMP for any reason at any time, or completely withdraw from the study (see [Section 9.3.4](#)). Subjects who consent will undergo the EoT/Follow-up assessment approximately 4 weeks after administration of the last dose of IMP.

At any time during this long-term extension study, subjects not deriving sufficient clinical benefit in the opinion of the Investigator should be discontinued from IMP. Investigators should monitor the clinical benefit of each subject in an ongoing manner throughout the study in order to make the determination as to whether it is appropriate for them to continue to participate.

IMP must be discontinued under the following circumstances and further steps need to be discussed with the medical monitor:

- A serious adverse event (SAE), drug reaction or complication, or an unacceptable AE, whether attributed to IMP or not, that precludes continuation of treatment with IMP. This includes the development of allergic reactions or the development of other potentially serious drug reactions to medication required by the protocol,
- Diagnosis of malignancy (except basal or squamous cell carcinoma) during study (treatment may be continued at the discretion of the subject and Investigator, and in consultation with the medical monitor),
- Subjects who develop suicidal behavior ([Section 12.4](#)),
- Evidence of pregnancy,
- Withdrawal of informed consent,
- Lost to follow-up,
- Significant non-compliance of the subject with study procedures,
- Decision of the Sponsor to terminate the subject, site, or the study.

The derivation of clinical response (at Week 52 for the Phase 2 parent study) will be made within the IVRS system using information provided by the study site. The IVRS system will determine the subject's eligibility to continue into the long-term extension study. Subjects who fail to meet eligibility criteria at the end of their parent study will not be eligible to continue to the long-term extension study in accordance with the IVRS instruction, and would continue in the Follow-up period of their parent study.

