### **11.1.2 Reporting of Serious Adverse Events**

All SAEs must be reported according to ICH GCP or local regulations, applying the regulation with the stricter requirements.

Investigators and other site personnel must inform the designated pharmacovigilance/safety services of any SAE that occurs during the course of the study (from the time of written informed consent until 30 days after the last EoT/Follow-up visit), whether or not it is considered causally related to the IMP or to the study procedure(s), and within 24 hours of when he/she becomes aware of it. An SAE with an onset day greater than 30 days from the EoT/Follow-up visit will be recorded only for fatal SAEs and those deemed by the Investigator to be drug-related or AESIs ([Section 11.1.1.3](#)). The Investigator should make every effort to obtain follow-up information on the outcome until the event is considered resolved, chronic and/or stable.

If a non-serious AE becomes serious, this and other relevant follow-up information must also be provided to the designated CRO within 24 hours as described above. The start date of the SAE is not the start date, but the date when the AE becomes serious; analogously, the stop date is the date when any seriousness criterion is no longer applicable, not the date when the AE is resolved.

All SAEs will also be recorded in the eCRF. The Investigator is responsible for informing the Ethics Committee of the SAE as per local requirements.

Paper SAE forms should be completed at the site and faxed/mailed to the designated pharmacovigilance/safety services or emailed to the global email distribution list within 24 hours of awareness of the event.

[figure not shown]
SAE and AESI reports should be sent or faxed to the designated pharmacovigilance/safety services provided in [Section 3](#).

There may be situations when an SAE (or AESI) has occurred and the Investigator has minimal information to include in the initial SAE report. However, it is very important that the Investigator always makes an assessment of causality for every event prior to transmission of the SAE Report Form. Minimum criteria are identifiable subject (number), a suspect product (i.e., IMP or concomitant medication), an identifiable reporting source (Investigator/study site identification), and an event or outcome that can be identified as serious. The Investigator may

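### Non-serious AEs are collected only to the EoT/Follow-up visit (nominally 4 weeks after the last dose for early withdrawers, 8 for completers), and most later events depend on unscheduled reporting

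*Protocol*

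**What the plan says.** **End of AE collection.** Protocol 11.1.1.8 counts a detrimental change as an AE from the first extension dose "up to completion of the EoT/Follow-up visit, should be considered an AE". Under 9.1.3.1.3, subjects who stop IMP early "return for the EoT/Follow-up assessment approximately 4 weeks after administration of their last dose of IMP"; 9.3.5 applies this to subjects who consent. Completers have their last dose at Week 200 and the follow-up visit at Week 208 (9.1.1, Table 9-1).

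**Serious events.** Protocol 11.1.2 requires any-cause SAE reporting "from the time of written informed consent until 30 days after the last EoT/Follow-up visit". SAEs with later onset are recorded only if fatal, judged drug-related by the investigator, or AESIs, with no end date. AESIs (11.1.1.3) are severe infections, malignancies, confirmed MACE and drug-related hypersensitivity, and are reported like SAEs. Section 11.1.1.8 also asks for notification of related SAEs at any time after the first dose.

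**Other post-dose periods in the Protocol.**
- Dosing (Table 9-1, note f): "IMP administration will occur on Day 1 of Week 0; followed by subsequent dosing Q12 weeks".
- Contraception (9.3.2): "the contraceptive method must be practiced for 16 weeks following final administration of IMP".
- Immunogenicity (9.1.3.1.3): "A final ADA sample needs to be collected after 20 weeks from last dose".
- Live vaccines (9.3.2, criterion 16): 10 weeks.

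Table 9-1 has no column after Week 208, so the 20-week ADA draw exists only as a footnote and a line of text, with no AE or concomitant-medication enquiry attached.

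**Analysis.** SAP 8.5.1 ends exposure on the last dose date. SAP 8.7.1 gives TEAEs a start but no end, and names no separate denominator for the rate per 100 subject-years.

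**The concern.** Incidence of all AEs and immunogenicity are primary objectives (Protocol 8.1). During treatment, AEs are asked about at every dosing visit, so each 12-week dosing interval is covered to its end. After the last dose, scheduled enquiry stops within that interval, and it stops sooner for subjects who leave early, the group that includes those who stopped because of an AE.

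Two kinds of event are then lost by rule: non-serious, non-AESI events after the EoT/Follow-up visit, and non-fatal, unrelated, non-AESI SAEs more than 30 days after it. Other late events may be missed in practice, because nobody is scheduled to ask. The immunogenicity objective has its own gap: a subject can be bled at 20 weeks for late antibodies with no record of symptoms or new medication since the last visit.

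**Working it through.** The plan states no follow-up target, so there is no planned figure to reproduce.

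**1. Windows after the last dose**
- AE, early withdrawer: 4 × 7 = 28 days. AE, completer: (208 − 200) × 7 = 56 days.
- Any-cause SAE: 28 + 30 = 58 days and 56 + 30 = 86 days.

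**2. Share of the Protocol's own post-dose periods that is covered** (window ÷ period, at most 100%)

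| Period | Days | AE, early | AE, completer | SAE, early | SAE, completer |
|---|---|---|---|---|---|
| Live vaccine, 10 wk | 70 | 40% | 80% | 83% | 100% |
| Dosing interval, 12 wk | 84 | 33% | 67% | 69% | 100% |
| Contraception, 16 wk | 112 | 25% | 50% | 52% | 77% |
| Final ADA sample, 20 wk | 140 | 20% | 40% | 41% | 61% |

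The any-cause SAE window closes 84 − 58 = 26 days before the dosing interval ends for an early withdrawer, and 86 − 84 = 2 days after it for a completer. The 84-day comparison is for the current Q12W regimen. The interval from Week 0 to Week 8 is shorter, and SAP 3.3 describes a Q4W arm before migration, for which 28 days is a full dosing interval.

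**3. Uncollected time**

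Inputs: N = 286 (Protocol 9.1.1, an upper limit). Assumed, because the documents give neither: early withdrawal d of 10%, 30% or 50%, and a mean last dose at Week 100 for those who stop.

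- Collected subject-years = 286 × [d × 104 + (1 − d) × 208] ÷ 52.18
- Uncollected to week h = 286 × [d × (h − 4) + (1 − d) × (h − 8)] ÷ 52.18
- Share = uncollected ÷ (collected + uncollected)

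| d | Collected | Uncollected to week 12 (early + completer) | Share | Uncollected to week 20 (early + completer) | Share |
|---|---|---|---|---|---|
| 10% | 1083 | 24.1 (4.4 + 19.7) | 2.2% | 68.0 (8.8 + 59.2) | 5.9% |
| 30% | 969 | 28.5 (13.2 + 15.3) | 2.9% | 72.3 (26.3 + 46.0) | 6.9% |
| 50% | 855 | 32.9 (21.9 + 11.0) | 3.7% | 76.7 (43.8 + 32.9) | 8.2% |

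Within early withdrawers the share is 8 ÷ (104 + 8) = 7.1% to week 12 and 16 ÷ (104 + 16) = 13.3% to week 20. Within completers it is 4 ÷ 212 = 1.9% and 12 ÷ 220 = 5.5%.

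**4. Effect on the rate if SAP 8.5.1 exposure is the denominator**

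With a constant event rate, the calculated rate is the true rate times (collection time ÷ exposure time). As the plan stands this is 104 ÷ 100 = 1.04 for an early withdrawer with a last dose at Week 100, and 208 ÷ 200 = 1.04 for a completer. Collecting to 20 weeks with the denominator unchanged gives 120 ÷ 100 = 1.20 and 220 ÷ 200 = 1.10. Extending collection without changing the SAP would therefore inflate the rate, more so in those who stop early.

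**The case against.** The strongest reply is that the most important late harms are not cut off. Deaths, drug-related SAEs, severe infections, malignancies, confirmed MACE and drug-related hypersensitivity remain reportable without an end date. A drug-related AE that led to discontinuation is followed until it resolves or stabilises (Protocol 11.1.1.1). A reader might infer from 11.1.1.8 alone that AE collection simply stops at the EoT/Follow-up visit; 11.1.1.3 and 11.1.2 do not support that. What remains is that the later route is passive. Apart from deaths, it turns on the investigator's causality opinion or on the AESI list, and following the event that led to stopping does not reveal new ones.

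Other points on that side also stand, wholly or in part:
- **Four weeks is nominal.** With visits 12 weeks apart, a subject who decides to stop at the next visit may already have been asked about AEs for about 12 weeks. Those who stop soon after a dose have the shortest window. Subjects who withdraw consent generally have no later contact at all.
- **The periods serve different purposes.** A reader might infer that the Protocol regards the drug as active for 12 to 20 weeks. It does not say so. Contraception is a precaution, the 20-week ADA time may reflect assay interference (SAP 8.8.2 sets a drug tolerance level of 6 µg/mL), and the live-vaccine period is 10 weeks. Even 10 weeks exceeds both AE windows, though, and the documents give no reason for 4.
- **The loss is not confined to those who stop.** Per subject it is larger for them, but in total completers contribute more uncollected time in the 10% and 30% rows above.
- **A bias in favour of the drug is a tempting inference, but it is not shown.** Exposure ends at the last dose while TEAEs have no end date, so missing post-dose time does not dilute the rate on that denominator. Events after stopping may also reflect a new treatment.

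**Conclusion.** The point holds as a gap in ascertainment. Scheduled AE enquiry ends inside the 12-week dosing interval for completers and early withdrawers on the current regimen, and nominally 4 weeks sooner after the last dose for early withdrawers. The any-cause SAE window also closes inside the interval for early withdrawers, but not for completers. Late symptoms cannot be systematically set against the 20-week ADA result.

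The size is modest: about 2-8% of total at-risk time, completers included, and about 7-13% within early withdrawers. These figures rest on 286 subjects, an assumed 10-50% early withdrawal, a mean last dose at Week 100 in those who stop, and visits at exactly 4 and 8 weeks. The consequence is under-counting of events. The effect on exposure-adjusted rates cannot be signed until the SAP states its denominator. The change is worth making because a later contact is already required.

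**What to change.** **Protocol 11.1.1.8, 11.1.2, 9.1.3.1.3 and Table 9-1.** Define one AE and SAE collection window counted from the last dose, the same for completers and early withdrawers. Let it run to the 20-week ADA contact. Record AEs, SAEs and concomitant medications there, including any new PsA therapy, by telephone if the draw is refused, except where consent has been withdrawn.

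**Table 9-1 and study duration.** Add a column for that contact. For a completer it falls at about Week 200 + 20 = 220, so reconcile it with the Week 208 end-of-study definition (Protocol 9.1.1) and the 208-week maximum duration (SAP 3.3). The existing ADA draw already conflicts with both.

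**SAP 8.5.1 and 8.7.1.** State the time at risk for the exposure-adjusted rate so that post-dose events and post-dose time match. Tabulate events after the last dose separately, flagged for new therapy.

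**Cost.** A protocol amendment, a SAP revision, one eCRF page and somewhat later safety close-out per subject. No new test is needed. Some late events will be confounded by subsequent treatment, which is why they should be shown separately.
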